Vital sign	X	X	X		X		X	X		Vital signs will also be taken at unscheduled office visits. Vital signs include body temperature, blood pressure, and pulse. Blood pressure and pulse will be measured in triplicate in the sitting position and should be measured prior to blood draws. Blood pressure will be assessed by utilizing a calibrated machine that will be provided to the sites.
Hematology	X		X					X		
Clinical chemistry ^a	X		X					X		Except for V1, chemistry labs require fasting (no food or drink, except water, for at least 8 hrs).
Urinalysis	X							X		
HbA1C	X							X		

Study Schedule, Protocol I5Q-MC-CGAM: SP I to SP III

Study Phase (SP)	SP I	SP II	SP III							
Description	Screening	Pre-Randomization Diary	Treatment						Comments	
Visit	1	2	3	4 (Phone visit)	5	6	7 (Phone visit)	8	9	Comments
Month						1		2	3	
Serum Pregnancy or FSH	X									Female patients only
Urine drug screen	X									
Randomization			X							
Immunogenicity			X		X	X		X	X	Immunogenicity samples must be collected prior to dose administration if the visit is a dosing visit. Samples will be taken in the event of early termination. The timing of samples will be recorded.
										CCI [REDACTED]
Plasma Storage Sample (K+/EDTA)	X	X	X		X	X		X	X	Samples must be collected prior to dose administration if the visit is a dosing visit. The timing of the samples will be recorded. These samples will be collected in an K+/EDTA container.
PK sampling					X	X		X	X	Samples must be collected prior to dose administration if the visit is a dosing visit. The timing of the samples will be recorded.
CCI [REDACTED]			C							[REDACTED]
RNA storage sample	X	X		X	X		X	X		Sample must be collected in a Tempus tube.

Study Schedule, Protocol I5Q-MC-CGAM: SP I to SP III

Study Phase (SP)	SP I	SP II	SP III							
Description	Screening	Pre-Randomization Diary	Treatment							Comments
Visit	1	2	3	4 (Phone visit)	5	6	7 (Phone visit)	8	9	Phone visits (V4 and V7) are contacts between office visits to collect any spontaneously reported AE after the first two injections of IP.
Month					1			2	3	
PGI-I					X			X	X	
C-SSRS/SHSF, SHFU	X	X	X		X			X	X	Should also be completed at unscheduled office visits.
Recording of AEs	X	X	X	X	X	X	X	X	X	
Review Diary data			X	X		X		X	X	Following Informed Consent, patients will be required to complete their diaries daily beginning the day of their next cluster headache attack. Sites should review the diary compliance with the patient during specified office visits.

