Efficacy analyses (measures derived from e-PRO)	Patients in ITT population with a baseline and at least one postbaseline observation	Visit 3	All Visits 4-11
TEAEs	GMB-treated population	Visits 1-3 before double-blind phase dosing for patients treated with GMB during SP III; Visits 1-9 before open-label phase dosing for patients treated with placebo during SP III.	All visits on or after first dosing of GMB up to Visit 22: Visit 3 after dosing to Visit 22 for GMB-treated patients during SP III; Visit 9 after dosing to Visit 22 for placebo treated patients during SP III.
SAEs, Discontinuations due to AEs	GMB-treated population	NA	All visits on or after first dosing of GMB up to Visit 22: Visit 3 after dosing to Visit 22 for GMB-treated patients during SP III; Visit 9 after dosing to Visit 22 for placebo treated patients during SP III.

Patient Population with Baseline and Postbaseline Definitions by Study Phase and Type of Analysis

Study Phase / Analysis	Patient Population	Baseline Observation	Postbaseline Observation(s)
C-SSRS categorical analyses	Patients in GMB-treated population with a baseline and at least one postbaseline C-SSRS assessment	Recent History: All Visits 1-3 excluding lifetime ^a for patients treated with GMB during SP III; Visits 1-9 for patients treated with placebo during SP III. All Prior History: Visits 1-3 including lifetime ^a for patients treated with GMB during SP III; Visits 1-9 for patients treated with placebo during SP III.	All visits after first dosing of GMB up to Visit 22: Visit 3.01-22 for GMB-treated patients during SP III; Visits 9.01-22 for placebo treated patients during SP III.
Treatment-emergent abnormal laboratory values	Patients in GMB-treated population with normal laboratory values at all nonmissing baseline visits (with respect to direction being analyzed) and who have at least one postbaseline observation	Visits 1-3 before double-blind phase dosing for patients treated with GMB during SP III; Visits 1-9 before open-label phase dosing for patients treated with placebo during SP III.	All visits after first dosing of GMB up to Visit 22: Visits 3.01- 22 for GMB-treated patients during SP III; Visits 9.01-22 for placebo treated patients during SP III.

Patient Population with Baseline and Postbaseline Definitions by Study Phase and Type of Analysis

Study Phase / Analysis	Patient Population	Baseline Observation	Postbaseline Observation(s)

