Treatment-emergent changes in vital signs and weight, ECG parameters	Patients in GMB-treated population with a baseline and at least one postbaseline observation	
For patients treated with GMB during SP III: Last non-missing value from Visits 1-3 for BP, pulse and ECG;
 
All Visits 1-3 for weight and temperature;
 
For patients treated with placebo during SP III: Last non-missing value from Visits 1-9 for BP, pulse and ECG;
 
All Visits 1-9 for weight and temperature.
	All visits after first dosing of GMB up to Visit 22: Visits 3.01-22 for GMB-treated patients during SP III; Visits 9.01-22 for placebo treated patients during SP III.
Treatment-emergent immunogenicity	Patients in GMB-treated population who are evaluable for TE ADA	Visit 3	All visits after first dosing of GMB up to Visit 22: All Visits 3.01-22 for GMB-treated patients during SP III; All Visits 9.01-22 for placebo treated patients during SP III.

Patient Population with Baseline and Postbaseline Definitions by Study Phase and Type of Analysis

Study Phase / Analysis	Patient Population	Baseline Observation	Postbaseline Observation(s)
Study Phase IV (Open-label Extension Phase)			
Efficacy analyses (PGI-I)	Open-label population		V16 and V22
Study Phase III, IV and V			
TEAEs	GMB-treated population	Visits 1-3 before double-blind phase dosing for patients treated with GMB during SP III; Visits 1-9 before open-label phase dosing for patients treated with placebo during SP III.	All visits on or after first dosing of GMB up to Visit 24: Visit 3 after dosing– Visit 24 for GMB-treated patients during SP III; Visit 9 after dosing to Visit 24 for placebo treated patients during SP III.
SAEs, Discontinuations due to AEs	GMB-treated population	NA	All visits on or after first dosing of GMB up to Visit 24: Visit 3 after dosing to Visit 24 for GMB-treated patients during SP III; Visit 9 after dosing to Visit 24 for placebo treated patients during SP III.

Patient Population with Baseline and Postbaseline Definitions by Study Phase and Type of Analysis

Study Phase / Analysis	Patient Population	Baseline Observation	Postbaseline Observation(s)

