C-SSRS categorical analyses	
Patients in GMB-treated population with a baseline and at least one postbaseline C-SSRS assessment
	
Recent History: All Visits 1-3 excluding lifetime^a for patients treated with GMB during SP III; Visits 1-9 for patients treated with placebo during SP III.
 
All Prior History: Visits 1-3 including lifetime^a for patients treated with GMB during SP III; Visits 1-9 for patients treated with placebo during SP III.
	
All visits after first dosing of GMB up to Visit 24: Visits 3.01-24 for GMB-treated patients during SP III; Visits 9.01- 24 for placebo treated patients during SP III.

Treatment-emergent abnormal laboratory values	
Patients in GMB-treated population with normal laboratory values at all nonmissing baseline visits (with respect to direction being analyzed) and who have at least one postbaseline observation
	
Visits 1-3 before double-blind phase dosing for patients treated with GMB during SP III; Visits 1-9 before open-label phase dosing for patients treated with placebo during SP III.
	
All visits after first dosing of GMB up to V24: Visits 3.01-24 for GMB-treated patients during SP III; Visits 9.01-24 for placebo treated patients during SP III.

Patient Population with Baseline and Postbaseline Definitions by Study Phase and Type of Analysis

Study Phase / Analysis	Patient Population	Baseline Observation	Postbaseline Observation(s)
Treatment-emergent changes in vital signs and weight, ECG parameters	Patients in GMB-treated population with a baseline and at least one postbaseline observation	For patients treated with GMB during SP III: Last non-missing value from Visits 1-3 for BP, pulse and ECG; All Visits 1-3 for weight and temperature; For patients treated with placebo during SP III: Last non-missing value from Visits 1-9 for BP, pulse and ECG; All Visits 1-9 for weight and temperature.	All visits after first dosing of GMB up to V24; Visits 3.01-24 for GMB-treated patients during SP III; Visits 9.01-24 for placebo treated patients during SP III.
Treatment-emergent immunogenicity	GMB-treated population with post-treatment ADA assessment who are evaluable for TE ADA.	Visit 3	All visits after first dosing of GMB up to Visit 24; All Visits 3.01-24 for GMB-treated patients during SP III; All Visits 9.01-24 for placebo treated patients during SP III.

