Abbreviations: ADA = anti-drug antibody; AE = adverse event; BP = blood pressure; C-SSRS = Columbia Suicide Severity Rating Scale; ECG = electrocardiogram; ePRO = electronic patient-reported outcome; GMB = galcanezumab; ITT = intent-to-treat; NA = not applicable; SAE = serious adverse event; TE ADA = treatment emergent anti-drug antibody; TEAE = treatment-emergent adverse event.

Note: Visit 3.01 indicates the first unscheduled visit occurring after Visit 3 and prior to Visit 4. Visit 9.01 indicates the first unscheduled visit occurring after Visit 9 and prior to Visit 10.

a Lifetime is captured in the C-SSRS Visit 1 case report form.

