ADA Not Present	ADA assay result is Not Detected and simultaneous drug concentration is at a level that has been demonstrated to not interfere in the ADA detection method (ie, drug concentration is below the assay's drug tolerance level). For patients receiving placebo, drug concentration is not assessed and is assumed to be below the assay's drug tolerance level.
ADA Inconclusive	ADA assay result is Not Detected but drug concentration in the sample is at a level that can cause interference in the ADA detection method.
ADA Not Detected with Drug Concentration Not Available	If drug concentration analysis was planned but result is not available for a treatment-period sample, a Not Detected sample will be declared ADA Not Detected with Drug Concentration Not Available. In the computation of Patient ADA status (see below, Section 5.5.9.1.6.2), these samples will be considered ADA Not Present, on the basis of prior knowledge that the drug tolerance level of the ADA assay is high relative to the expected drug concentration levels.
ADA Missing	ADA sample not drawn, QNS, not tested, etc., causing there to be no laboratory result reported or the result is reported as "no test".

Sample Clinical ADA Interpretation Results (Abbreviation)

Abbreviation: ADA = anti-drug antibody.

Parallel terminology applies for NAb Detected, NAb Not Detected, NAb Present, NAb Not Present, NAb Inconclusive, NAb Not Detected with Drug Concentration Not Available, and NAb Missing. Anti-drug antibodies and NAb are distinct assays and have different assay operating characteristics.

5.5.9.1.6.2. Definitions of Patient ADA Status

Patient evaluable for TE ADA: A patient is evaluable for TE ADA if the patient has a non-missing baseline ADA result, and at least 1 non-missing postbaseline.

TE ADA positive (TE ADA+) patient: A patient who is evaluable for TE ADA is TE ADA+ if either of the following holds:

- **Treatment-induced:** The patient has baseline status of ADA Not Present and at least one postbaseline status of ADA Present with titer ≥ 20 (that is, 2^*MRD where for this ADA assay the MRD, the minimum required dilution of the ADA assay, is 10).
- **Treatment-boosted:** The patient has baseline and postbaseline status of ADA Present, with the postbaseline titer being 2 dilutions (4-fold) greater than the baseline titer. That is, the patient has baseline status of ADA Present, with titer 1:B, and at least one postbaseline status of ADA Present, with titer 1:P, with P/B ≥ 4 .

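### For patients who cross from placebo to galcanezumab at Visit 9, treatment-emergent ADA is judged against Visit 3, so antibody that arose on placebo can be counted as induced by galcanezumab

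*SAP*

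**What the plan says.** SAP section 5.5.9.1.6.3 refers to Table CGAM.5.3 for the baseline and postbaseline periods of the ADA analyses. For SP III/IV combined, the row reads "Patients in GMB-treated population who are evaluable for TE ADA Visit 3 All visits after first dosing of GMB up to Visit 22", and the window then divides by SP III treatment: "All Visits 3.01-22 for GMB-treated patients during SP III; All Visits 9.01-22 for placebo treated patients during SP III". The row for SP III/IV/V combined has the same Visit 3 baseline and ends "All Visits 3.01-24 for GMB-treated patients during SP III; All Visits 9.01-24 for placebo treated patients during SP III". The table's note says that "Visit 9.01 indicates the first unscheduled visit occurring after Visit 9 and prior to Visit 10".

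Other rows for the same population treat former placebo patients differently. For TEAEs and laboratory values their baseline is "Visits 1-9 before open-label phase dosing for patients treated with placebo during SP III". For vital signs and ECG the entry is "For patients treated with placebo during SP III: Last non-missing value from Visits 1-9 for BP, pulse and ECG", and all Visits 1 to 9 serve for weight and temperature. The C-SSRS row also runs to Visit 9.

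Section 5.5.9.1.6.2 defines the treatment-induced category: "The patient has baseline status of ADA Not Present and at least one postbaseline status of ADA Present with titer" of at least 20. Treatment-boosted needs at least a 4-fold rise over a positive baseline. A patient without a baseline result is not evaluable.

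The protocol's Study Schedule (Attachment 1) places SP III immunogenicity samples at Visits 3, 5, 6, 8 and 9 and states: "Immunogenicity samples must be collected prior to dose administration if the visit is a dosing visit".

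**The concern.** A treatment-emergent finding should be new or worse relative to the patient's state just before first exposure. For patients given saline placebo in SP III, first exposure is the open-label dose at Visit 9. The two rows start their postbaseline window after that visit but leave the baseline at Visit 3. The galcanezumab-free samples at Visits 5, 6, 8 and 9 therefore play no part in either row. Reactivity that appeared in those three months and persisted is attributed to galcanezumab.

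The development of ADA in exposed patients is a stated secondary objective. The galcanezumab-treated summaries pool everyone into a single group with no placebo column beside it, so the table itself would not reveal background reactivity. The baseline-to-maximum titre shift and the follow-up-cohort summaries draw on the same baseline.

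**Working it through.** **1. Is a Visit 9 pre-dose sample planned?** The immunogenicity rows of the Study Schedule give Visits 3, 5, 6, 8 and 9 in SP III (5 samples), Visits 13, 19 and 22 in SP IV (3), and Visits 23 and 24 in SP V (2). 5 + 3 + 2 = 10, which equals the maximum of 10 immunogenicity samples in protocol Attachment 4. Visit 9 is a dosing visit for patients entering SP IV, so its sample precedes the first open-label dose. SAP Table CGAM.5.9 assumes that drug concentration in placebo patients is below the assay's tolerance level, so this sample can be interpreted.

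**2. Where does that sample go?** It is not baseline (Visit 3 only), and it falls before the window that opens at 9.01. It is therefore unused in both galcanezumab-treated rows.

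**3. Does the choice change the classification?** Illustrative titres for a patient on placebo in SP III, under the rules of section 5.5.9.1.6.2:

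| Visit 3 | Visit 9 pre-dose | Visit 13 | Visit 3 baseline | Visit 9 baseline |
|---|---|---|---|---|
| Not present | 1:40 | 1:40 | TE ADA+ (induced; 40 ≥ 20) | Not TE ADA+ (40/40 = 1 < 4) |
| 1:10 | 1:40 | 1:40 | TE ADA+ (boosted; 40/10 = 4) | Not TE ADA+ (40/40 = 1 < 4) |
| 1:20 | Not present | 1:40 | Not TE ADA+ (40/20 = 2 < 4) | TE ADA+ (induced; 40 ≥ 20) |

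The first two cases are false positives under the SAP; the third is a missed case. A patient with no Visit 3 result is also lost as unevaluable, even with a valid Visit 9 sample.

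**4. How many patients could be affected?** The protocol synopsis plans 162 randomised and 146 completing SP III; allocation is 1:1.

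- Galcanezumab arm: 162/2 = 81, assuming all are dosed.
- Placebo completers: 146/2 = 73. Only completers may enter SP IV, and entry is optional, so on planned numbers 73 is the ceiling.
- Galcanezumab-treated population with full roll-over: 81 + 73 = 154. Placebo share: 73/154 = 47%.
- With 80% roll-over: 0.8 × 73 = 58.4; 81 + 58.4 = 139.4; share 58.4/139.4 = 42%.

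Let q be the proportion of roll-over patients whose ADA arises on placebo and still meets the titre rule after Visit 9. The documents do not give q; 1–4% is an assumption.

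| q | Full roll-over: 73q patients | Share of 154 | 80% roll-over: 58.4q patients | Share of 139.4 |
|---|---|---|---|---|
| 1% | 0.73 | 0.5 points | 0.58 | 0.4 points |
| 4% | 2.92 | 1.9 points | 2.34 | 1.7 points |

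With full roll-over and q = 1%, the chance of at least one such patient is 1 − 0.99^73 = 52%. At q = 10% the count would be 7.3 patients, or 4.7 points.

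**The case against.** The strongest case is that this is a small matter in a descriptive summary.

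- The placebo patients' samples from Visits 5 to 9 are used elsewhere. They are the postbaseline data of the SP III analysis, which compares the arms by Fisher's exact test. This is correct, but it means that a persisting conversion is reported twice: under placebo in SP III and under galcanezumab in the pooled summary.
- The planned listings of patients with TE ADA or with ADA present at any time would allow such a patient to be traced. They would not correct the incidence table.
- The antibody must last. The next scheduled sample after Visit 9 (day 90) is Visit 13 (day 180), and it must meet the titre rule. This limits the number of cases, and the assumed rate is defined to include it.
- The main error overstates galcanezumab's immunogenicity and so does not hide a signal. The reverse case can also occur, so the direction is not guaranteed.
- With a Visit 9 baseline, a patient already positive at Visit 9 could count only through a 4-fold rise. That is how the boosted category is meant to work.

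The protocol (section 12.2.1) permits a Visit 9 baseline for some analyses, but the SAP does not assign one to ADA. The SAP's rule of taking the last value before the phase of interest is written only for blood pressure, pulse and ECG. Nothing elsewhere repairs the two rows.

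**Conclusion.** The concern holds. As written, the two galcanezumab-treated TE ADA rows can attribute antibody that predates exposure to galcanezumab. They also depart, without a stated reason, from the convention used in the other treatment-emergent rows for this population. The Visit 3 entry is the same in both rows, so a table-reading error is unlikely.

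The likely size is about 1–3 misclassified patients, or 0.5–1.9 percentage points. This rests on the planned minimum sample size, full roll-over of 73 placebo completers and an assumed persistent conversion rate of 1–4%. Lower roll-over reduces the count, and a larger trial after the interim analysis would raise it. The SP III between-arm ADA comparison and all efficacy analyses are unaffected. The point should be corrected because it bears on a stated secondary objective, but it does not threaten the trial's conclusions.

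**What to change.** In both galcanezumab-treated TE ADA rows of Table CGAM.5.3 (SP III/IV and SP III/IV/V), define baseline as the last non-missing ADA result before the patient's first galcanezumab dose. On the planned schedule this is Visit 3 for patients given galcanezumab in SP III and normally the Visit 9 pre-dose sample for patients given placebo. Tie the rule to the first galcanezumab dose rather than to randomised arm, because this population is defined by treatment received and the SAP foresees incorrect administration.

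Use the same baseline for evaluability, the titre shift table and the follow-up-cohort summaries. State explicitly that the last pre-dose result is used, rather than all pre-dose results.

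The cost is two table cells and one dataset derivation; no new samples are needed. The pooled summary would then combine baselines taken at different visits, as the other safety rows already do; a table footnote should say so.

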5.5.2. Patient Disposition

The number and percentage of ITT patients who complete the study or discontinue early will be tabulated for all treatment groups for SP III, SP IV, and SP V, both overall and by visit. Reasons for discontinuation will be compared between treatment groups using Fisher's exact test for SP III with the ITT population. Descriptive statistics only will be presented for the treatment groups in SP IV and SP V. For patients who were randomized without drug injection, reasons for early discontinuation will be provided in a listing.

Patient allocation by investigator will be summarized for SP III for all ITT patients.

Patient allocation by investigator will also be listed for all study phases.

5.5.3. Important Protocol Deviations

Important protocol deviations that potentially compromise the data integrity and patients' safety will be summarized by treatment for the ITT population.

Section 7 ([Appendix 2](#)) lists the categories, subcategories, study-specific terms of important protocol deviations and source of identification. Per study team's discretion, for non-programmable protocol deviations, additional categories and subcategories other than the ones in [Appendix 2](#) can always be added into the final non-programmable protocol deviations list as deemed necessary.

Tables and listings of subjects with important protocol deviations will be provided for the ITT population.

5.5.4. Patient Characteristics

The following patient characteristics at baseline will be summarized by treatment group for all ITT patients.

- demographic (age, gender, race, ethnicity, country, region, height, weight, body mass index)
- baseline disease characteristics:
 - number of weekly cluster headache attacks
 - average severity of cluster headache pain for the cluster headache attack days
 - weekly total cluster headache attack duration
 - weekly number of times of using oxygen
 - weekly number of times of using oral triptan, sumatriptan nasal spray, or zolmitriptan nasal spray
 - weekly number of times of using sumatriptan Sc
 - weekly number of times of using acetaminophen/paracetamol or NSAIDs
 - number of times of using oxygen per cluster headache attack

- number of times of using oral triptan, sumatriptan nasal spray, or zolmitriptan nasal spray per cluster headache attack
- number of times of using sumatriptan Sc per cluster headache attack
- number of times of using acetaminophen/ paracetamol or NSAIDs per cluster headache attack
- total weekly dose for oral triptan, sumatriptan nasal spray, and zolmitriptan nasal spray combined
- total weekly dose for sumatriptan Sc
- total weekly dose for oral triptan
- total weekly dose for sumatriptan nasal spray
- total weekly dose for zolmitriptan nasal spray
- prior cluster headache history in last 7 days prior to Visit 1
- baseline alcohol, tobacco, caffeine, and nicotine consumption
- medical history and pre-existing conditions

Comparisons between treatment groups will be performed using Fisher's exact test for categorical data and analysis of variance (ANOVA) with treatment and pooled investigative site as independent variables in the model for continuous data.

Medical history and pre-existing conditions will be summarized by descending frequency of Preferred Term (PT) within System Organ Class (SOC) and by descending frequency of PT respectively, and comparison between treatment groups will be performed using Fisher's exact test. Medical history is defined as illness(es) that ended prior to the signing of informed consent. Pre-existing conditions are medical events ongoing at the time of informed consent.

5.5.5. *Exposure to Investigational Product*

Patients will receive the investigational product (IP) at Month 0, 1, 2, 3, ..., up to Month 14.

The following information will be recorded on the electronic case report form (eCRF) for each dose:

- confirmation that the patient received the IP
- date and time of administration

